4.4.2.1.2. Safety Results

During the performance of the TDS-IM V1.0 study, there were no significant safety concerns involving the investigational products. Overall, 30/31 (96.8%) subjects receiving at least 1 dose of HTNV DNA, PUUV DNA, or HTNV/PUUV DNA vaccines reported at least 1 AE. Of the 246 AEs reported, 96.7% were graded as mild to moderate. Seven out of 8 AEs identified as either Grade 3 or Grade 4 were considered unrelated to the study vaccine; 1 Grade 3 AE was considered unlikely to be related. There were 2 SAEs reported during this study, both involving transient Grade 4 laboratory abnormalities detected in otherwise asymptomatic individuals (hypoglycemia and hyperkalemia, respectively). Each event was evaluated and determined to be unrelated to study participation.

Seventy-six incidents of injection site pain were reported in 28/31 (90.3%) subjects, accounting for 30.9% of all AEs. The other most commonly reported AEs were headache (5.7%), injection site bruising (3.7%), muscle aches (3.3%), and fatigue (3.3%). Ninety-six/246 (39.0%) AEs were

considered related to injection, of which 87 (90.6%) were local reactions at the injection site (pain, bruising, or erythema).

4.4.2.2. A Phase I, Randomized, Observer-blind, Placebo Controlled Study to Assess the Safety, Reactogenicity, and Immunogenicity of a Venezuelan Equine Encephalitis DNA Vaccine Candidate Administered Intramuscularly or Intradermally by Electroporation to Healthy Adults (NCT01984983)

In a Phase 1, randomized, double-blind, placebo-controlled study, a DNA-based Venezuelan Equine Encephalitis vaccine, pWRG/VEE, or placebo control was administered to 41 healthy, adult subjects using either the Ichor TDS-IM V1.0 or TDS-ID EP devices ([Hannaman, et al, 2016](#)). Subjects received up to 3 administrations of the pWRG/VEEV vaccine. Subjects in the TDS-IM V1.0 groups received 0.5 mg (N = 8) or 2.0 mg (N = 9) of pWRG/VEE or a saline placebo (N = 4) in a 1.0-mL injection. Subjects in the TDS-ID groups received 0.08 mg (N = 8) or 0.3 mg (N = 8) of pWRG/VEE or a saline placebo (N = 4) in a 0.15-mL injection. Subjects were monitored for a total of 360 days.

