4.5.1.1. Local Reactions

Local reactions in previous studies have included pain, stinging, itching, bruising, tingling, numbness and redness at the injection site (deltoid muscle or associated skin in that area of the arm), and sometimes affecting the arm distal to the site. Information about local reactions are described below for each device type.

TDS-IM V1.0 Device:

Adverse reactions associated with the use of the TDS-IM V1.0 device for DNA vaccine delivery and reported in almost all subjects include acute pain with localized muscle contractions during the application of the electrical fields. In the TDS-IM V1.0 study of the hantavirus DNA vaccines, brief, but intense, muscle contractions and associated local pain/discomfort during the period of EP administration were observed in essentially all subjects. Additional AEs associated with the administration procedure included minor, transient cutaneous bleeding at the sites of electrode and injection needle penetration, and mild to moderate injection site soreness/bruising typically lasting for 24 to 72 hours, but in a small number of cases, up to 7 days post administration. Occasionally, subjects have also reported mild, transient paresthesia (tingling) or hypoesthesia (numbness) in the injected limb or fingers for a few seconds or minutes following electric field application. Over the 24-72 hours after administration, administration site soreness, erythema, induration and/or eschar formation of mild to moderate severity are commonly reported. Other injection site findings of mild severity including bruising and/or hematoma have been reported occasionally. The associated injection site reactions have typically been of mild to moderate severity and typically resolve within 24-72 hours following administration. However, in rare instances, subjects have reported severe local site soreness which resolved by 48 hours post administration.

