To date, the TDS-ID device has been used as the means of DNA vaccine administration in one completed and 2 ongoing clinical studies sponsored by Ichor. The results of the VEEV DNA vaccine study have been published (Hannaman et al, 2016). Adverse reactions associated with the use of the TDS-ID device include acute pain at the time of electroporation application in almost all subjects. Mild, transient bleeding at the sites of electrode penetration was commonly observed following removal of the device. These included injection site pain, erythema, induration, swelling, tenderness, bruising, punctures at the site of needle penetration, eschar formation at the site of needle penetration, and/or localized pigmentation changes. The associated injection site reactions typically resolved within 24-72 hours following administration.

Consistent with the clinical safety experience from the VEEV DNA vaccine study, interim safety reports from the 2 ongoing clinical studies utilizing the TDS-ID device (clinicaltrials.gov # NCT02589795 and EUDRA CT# 2014-001997-33) have included mild to moderate injection site reactions including minor bruising and hematoma at the sites of administration.

No serious adverse events attributed to the device or administration procedure have been observed to date during any of the clinical studies utilizing the TDS-ID device.

Tolerability of TDS-IM V1.0 compared to TDS-ID device:

In the VEEV DNA vaccine study, which compared IM and ID-EP delivery, the results of a subject questionnaire revealed that the IM- and ID-EP procedures were both considered to be generally acceptable for prophylactic vaccine administration, with the acute tolerability of ID EP delivery judged to be greater than that of IM-EP delivery published ([Hannaman et al, 2016](#)).

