6.3. Measures Taken to Minimize/Avoid Bias

6.3.1. Randomization

A randomization plan will be used to allocate subjects into experimental groups, per the study priorities described in Section 6.2. In addition, as of Version 5.0, ten replacement subjects will be enrolled into Group 6. A fixed random allocation will ensure that the groups are balanced in size at the end of experiment.

Designated study personnel (excluding the principal investigator [PI] and other investigators) will fill the vaccine cohorts as potential subjects successfully complete the screening process and are deemed eligible to participate by the PI (or another designated investigator). For the purposes of this study, the groups will be defined as follows, and each subject will receive one dose of vaccine on Days 0, 28, and 56.

Group 1 (12 subjects): HTNV by ID EP

Group 2 (12 subjects): HTNV by IM EP

Group 3 (12 subjects): PUUV by ID EP

Group 4 (12 subjects): PUUV by IM EP

Group 5 (12 subjects): HTNV/PUUV by ID EP

Group 6 (22 subjects): HTNV/PUUV by IM EP

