11.3. Level of Significance to Be Used

All statistical analyses will be made using a two-tailed $\alpha = 0.05$.

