4. INVESTIGATIONAL PLAN

4.1. Overall Study Design

The study design, including doses and schedule, is based on the experience of a team of investigators to include personnel at USAMMDA (now ORA), USAMRIID, Ichor, and WRAIR, who have performed clinical trials with similar DNA vaccine constructs using Ichor's TDS-IM EP device for DNA vaccinations. These TDS-IM and TDS-ID EP devices have been tested in humans previously in a recent clinical trial to evaluate the safety and immunogenicity of a DNA vaccine for Venezuelan encephalitis virus. These same HTNV and PUUV DNA vaccine products have also been tested in humans previously, albeit only using the TDS-IM EP device, and at lower dose levels than proposed in this study. Previous studies examined these vaccines in Phase 1 and 2 clinical trials at up to 2-mg dose levels per IM EP administration, whereas this study is testing up to 6 mg of DNA per administration using the 2 devices. The GLP repeat-dose rabbit toxicology and immunogenicity study performed in support of this study administered these same HTNV and PUUV DNA vaccines at up to 6 mg doses using the 2 devices and at an increased dosing frequency compared to this proposed Phase 1 clinical trial design. The rabbit toxicology study did not reveal safety concerns for the use of this higher dose level and with these 2 devices.

This study will be a single-center, randomized, study of the HTNV, PUUV, and combined HTNV/PUUV DNA vaccines delivered IM and ID by EP.

Pending sentinel group outcomes (elaboration in Section 4.2.1), the study will enroll up to 6 randomized groups of up to 12 subjects each for a total of up to 72 subjects (12 enrolled in effort to ensure at least 10 will complete per group). The HTNV and PUUV DNA vaccines will be administered to subjects as follows:

Group 1: 0.6 mg HTNV by ID EP

Group 2: 3.0 mg HTNV by IM EP

Group 3: 0.6 mg PUUV by ID EP

Group 4: 3.0 mg PUUV by IM EP

Group 5: 1.2 mg HTNV/PUUV by ID EP

Group 6: 6.0 mg HTNV/PUUV by IM EP

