6.7. Multiple Comparisons/Multiplicity

Multiplicity adjustments are not planned.

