TABLE 3.1: Proportion of Seropositive Subjects at Each Blood Collection Time Point

Collection Point	Group 1 (N=X)		Group 2 (N=X)		Group 3 (N=X)		Group 4 (N=X)		Group 5 (N=X)		Group 6 (N=X)	
	n	%	n	%	n	%	n	%	n	%	n	%
1	x	xx										
	[x,x]		[x,x]		[x,x]		[x,x]		[x,x]		[x,x]	
2												
3												
4												
5												
6												
7												

Note: 95% confidence intervals for sample proportion in brackets

TABLE 3.2: Proportion of Subjects that Ever Seroconverted at Each Blood Collection Time Point

Collection Point	Group 1 (N=X)		Group 2 (N=X)		Group 3 (N=X)		Group 4 (N=X)		Group 5 (N=X)		Group 6 (N=X)	
	n	%	n	%	n	%	n	%	n	%	n	%
1	x	xx										
	[x,x]		[x,x]		[x,x]		[x,x]		[x,x]		[x,x]	
2												
3												
4												
5												
6												
7												

Note: 95% confidence intervals for sample proportion in brackets

TABLE 3.3: Duration of Seropositivity if Ever Seroconverted

	Group 1 (n=x)	Group 2 (n=x)	Group 3 (n=x)	Group 4 (n=x)	Group 5 (n=x)	Group 6 (n=x)
Mean						
Standard Deviation						
95% CI for Mean						
1st Quartile						
Median						
3rd Quartile						
Min						
Max						

TABLE 3.4: Geometric Mean Titers of the PsVNA50 at Each Blood Collection Time Point

Collection Point	Group 1 (N=X)		Group 2 (N=X)		Group 3 (N=X)		Group 4 (N=X)		Group 5 (N=X)		Group 6 (N=X)	
	μ	SD										
1	x	x	x	x	x	x	x	x	x	x	x	x
	[x,x]		[x,x]		[x,x]		[x,x]		[x,x]		[x,x]	
2												
3												
4												
5												
6												
7												

Note:

- μ = mean; SD = standard deviation
- 95% confidence intervals for sample proportion in brackets

TABLE 4.1: Safety Analysis Group Comparison: Ever Experienced Solicited Adverse Events

Group:	1	2	3	4	5	6	P-value ¹
N=	x	x	x	x	x	x	
% Reporting	xx	xx	xx	xx	xx	xx	
(95% CI)	(x,x)	(x,x)	(x,x)	(x,x)	(x,x)	(x,x)	
Pair 1	•	•					x
Pair 2		•	•				x
Pair 3				•	•		x
Pair 4	•				•		x
Pair 5		•			•		x
Pair 6		•				•	x
Pair 7			•		•		x

¹P-value obtained from a two-sided Fisher's exact test

TABLE 4.2: Safety Analysis Group Comparison: Ever Experienced Unsolicited Adverse Events

Group:	1	2	3	4	5	6	P-value ¹
N=	x	x	x	x	x	x	
% Reporting (95% CI)	xx (x,x)	xx (x,x)	xx (x,x)	xx (x,x)	xx (x,x)	xx (x,x)	x
Pair 1	•	•					x
Pair 2		•	•				x
Pair 3				•	•		x
Pair 4	•			•			x
Pair 5		•		•			x
Pair 6	•				•		x
Pair 7			•		•		x

¹P-value obtained from a two-sided Fisher's exact test

TABLE 4.3: Immunogenicity Analysis: Ever Seroconverted

Group:	1	2	3	4	5	6	P-value ¹
N=	x	x	x	x	x	x	

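### The SAP's only p-values for solicited AEs rest on an any-grade, ever/never outcome that is probably near its ceiling, so a non-significant result says little about reactogenicity

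*SAP*

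**What the plan says.** SAP Appendix I contains "TABLE 4.1: Safety Analysis Group Comparison: Ever Experienced Solicited Adverse Events". The shell gives each group's percentage with a 95% CI and seven pairwise p-values, footnoted as two-sided Fisher's exact tests. No grade, symptom or dose is specified, so I read the outcome as any solicited AE of any grade after any of the three injections.

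Solicited AEs (SAP 8.5.3, Protocol 10.3.2) include injection-site pain, tenderness, redness, swelling and bruising, together with fever, myalgia, headache, fatigue and others. They are counted from each injection through 14 days.

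On significance, Protocol 11.3 says "All statistical analyses will be made using a two-tailed" alpha of 0.05, and SAP 6.7 says "Multiplicity adjustments are not planned". On group size, SAP 4.1 has "12 enrolled in effort to ensure at least 10 will complete per group", while Protocol 6.3.1 now has "Group 6 (22 subjects): HTNV/PUUV by IM EP".

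On expected rates, Protocol 4.4.2.1.2 reports for the earlier IM study: "Seventy-six incidents of injection site pain were reported in 28/31 (90.3%) subjects, accounting for 30.9% of all AEs". Protocol 4.5.1.1 says of the ID device: "Adverse reactions associated with the use of the TDS-ID device include acute pain at the time of electroporation application in almost all subjects". Of the IM device in the hantavirus vaccine study it says: "brief, but intense, muscle contractions and associated local pain/discomfort during the period of EP administration were observed in essentially all subjects".

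Severity is tabulated elsewhere. SAP Table 2.3.2 gives maximum grade by symptom and group, repeated for each dose, without a test.

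**The concern.** The primary objective is safety and reactogenicity of three formulations by two routes. If nearly every subject in every group has some injection-site pain, an ever/never outcome takes almost the same value everywhere. It then carries no information on whether one route or the combination produces more moderate or severe reactions, or more fever, fatigue or myalgia. Local pain fills the pooled outcome and hides the systemic part of it.

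At stake is the interpretation. A column of non-significant p-values under a safety group comparison heading invites the conclusion that the groups are similar, when the outcome had little chance of showing otherwise.

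**Working it through.** **Inputs.** The rate anchors are from Protocol 4.4.2.1.2: injection-site pain in 28/31 and any AE in 30/31. Group sizes are 12 (10 if only completers count) and 22 for Group 6. The test is two-sided Fisher at 0.05, unadjusted.

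**Reproducing the plan's figures.** 28/31 = 0.903 and 30/31 = 0.968, as stated. The exact (Clopper-Pearson) 95% CI for 28/31 is 74.2% to 98.0%. Any solicited AE must be at least as frequent as pain alone in the same subjects. The 96.8% covers any AE, solicited or not. I therefore use 90% and 97% as a plausible range. This is an assumption, since the documents give no any-solicited rate.

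**What the test needs to reach p<0.05.** If one group of 12 is at 12/12 and the other has k subjects without an event, the probability that all k fall in that second group is C(12,k)/C(24,k). The two-sided p is twice this for equal groups.

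- 12/12 v 9/12: 2 × 220/2,024 = 0.217
- 12/12 v 8/12: 2 × 495/10,626 = 0.093
- 12/12 v 7/12: 2 × 792/42,504 = 0.037

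The second group must therefore be at 7/12 (58%) or lower. At 10 v 10, 10/10 needs 5/10 or lower (p=0.033; 6/10 gives 0.087). With Group 6, 22/22 v 9/12 gives C(12,3)/C(34,3) = 220/5,984 = 0.037. The opposite tail is more probable than this and is not added. 22/22 v 10/12 gives 0.118.

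**Power.** This is the sum, over all pairs of counts (a, b) with Fisher p ≤ 0.05, of Bin(a; n1, p1) × Bin(b; n2, p2).

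| True rates | Sizes | Power |
|---|---|---|
| 97% v 90% | 12 v 12 | 0.3% |
| 97% v 80% | 12 v 12 | 5% |
| 97% v 90% | 10 v 10 | 0.1% |
| 97% v 80% | 10 v 10 | 2% |
| 97% v 90% | 22 (Group 6) v 12 | 7% |
| 97% v 80% | 22 (Group 6) v 12 | 30% |
| 97% v 80% | 12 v 22 (Group 6 lower) | 9% |

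**Same ever-rate, different severity.** The documents give no rates by grade, so these are assumed. Let two groups of 12 each have a 95% ever-rate, with Grade 2 or higher at 20% and 65%. The Table 4.1 test is significant 0.02% of the time. Fisher on Grade 2 or higher has 50% power (33% at 10 v 10).

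**Limits of the alternative.** If Grade 2 or higher events are uncommon, Fisher power at 12 v 12 is 4% for 5% v 20%, about 10% for 10% v 30%, and 21% for 20% v 50%.

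**What the other tables cover.** Table 2.3.2 has grade by symptom and group, but dose by dose, with all injection-site reactions in one row and an any-symptom row that mixes local with systemic. Table 2.2 separates local from systemic but has no group columns. No SAP table shown in the text gives any-local or any-systemic solicited AEs by group across doses.

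**The case against.** The best defence is that the plan does not lean on these p-values. SAP 5 calls all analyses exploratory and says group sizes were not chosen for power. Protocol 11.2 says the study is not designed to show significant differences between groups. Table 4.1 prints each group's percentage and CI, so a ceiling would be visible. This stands, and it keeps the point at the level of a cheap improvement. It does not explain why the one tested outcome should be the one least able to differ.

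A reader might also infer four stronger things that the documents do not support.

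- *That this is the only between-group safety test.* Protocol 11.1.1 adds Fisher tests on AEs within body systems and analysis of variance on vital signs, including respiratory rate (tachypnea is a solicited AE). SAP Table 4.2 tests unsolicited AEs, where eschar, bleeding, tingling or numbness and pigmentation changes are counted. Table 4.1 is the SAP's only p-value for solicited AEs, and nothing wider should be claimed.
- *That severity or systemic events go unreported by group.* Table 2.3.2 reports both, symptom by symptom, and Table 2.1 covers injection pain by group.
- *That a ceiling is established in all six groups.* The measured rate comes from 31 IM subjects at a lower dose. The ID evidence is qualitative, and acute ID tolerability was judged better than IM. The documents do not say whether momentary pain during the pulse is recorded as a solicited AE.
- *That the test cannot separate groups, or will give p-values all near 1.* A group at or below 58% would separate from 12/12, 12/12 v 9/12 gives p=0.22, and Group 6 at 22/22 separates from 9/12.

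Finally, a Grade 2 cut is one choice among several, and splitting local from systemic doubles the unadjusted comparisons. Both remarks are fair, so the fix should lead with estimates rather than tests.

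**Conclusion.** The point holds as a limit on what Table 4.1 can show. If any-grade solicited AE rates are about 90% to 97%, its p-values are very unlikely to separate the groups, whatever the differences in severity or systemic events. The exception with appreciable power is a comparison in which Group 6 (22 subjects) has the higher rate and the other group is clearly lower. A non-significant result should not be reported as similar reactogenicity.

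The conclusion assumes that this trial's rates resemble the earlier IM study, that ID rates are also high, and that the outcome pools all grades and doses as the title implies. If ID rates prove much lower, for example below 58% against a full IM group, the test could detect it.

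**What to change.** In SAP Table 4.1, replace the compared outcome with solicited AEs of Grade 2 or higher, in two panels, local and systemic. For each, give the group proportions and the pairwise differences with 95% CIs. Label any p-values exploratory and unadjusted. Keep any grade as a descriptive row with its CI and no p-value. Add a sentence that a non-significant comparison is not evidence of similar reactogenicity.

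The cost is a change to the table shell and derived variables from data already collected (grade, and local or systemic type). The comparisons rise from 7 to 2 × 7 = 14 without multiplicity control, and if Grade 2 or higher events are uncommon the intervals will be wide and power still low.

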10.6.1. Methods/Timing for Assessing, Recording, and Analyzing Safety Endpoints

AEs, solicited AEs, and SAEs will be assessed at all study visits, documented in the source records, and recorded on the eCRFs using accepted medical terms and/or the diagnoses that accurately characterize the event. When a diagnosis is known, the AE term recorded on the eCRF will be the diagnosis rather than a constellation of symptoms. The investigator will assess all AEs for seriousness, relationship to investigational product, severity, and other possible etiologies. When an adverse event has not resolved by study closure, it will be documented on the AE eCRF as "ongoing."

The time frame for the collection of AEs and SAEs begins at the first administration of investigational product through the end of the study.

The timeframe for the collection of solicited AEs begins at the first administration of investigational product through 14 days following each dose of investigational product (the first 14 days will be assisted with a memory aid).

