3.3. Primary Endpoints

The primary endpoints align with the safety objective. The nature, frequency, and severity of adverse events (AEs) and/or serious adverse events (SAEs) associated with TDS-EP-based administration of HTNV and PUUV DNA vaccines.

- The occurrence of solicited local and systemic AEs occurring from the time of each injection through 14 days following the procedure (memory aid to assist with the first 14 days)
- The occurrence of vaccine-related unsolicited AEs from the time of the first injection through 28 days following each injection
- The occurrence of SAEs from the time of the first injection through the final study visit for each subject (approximately 6 months post-last vaccination)
- The occurrence of clinical safety laboratory AEs through 14 days following each study vaccination.

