4.3. Study Sample

The study sample will consist of up to 72 healthy male and nonpregnant, nonlactating female subjects, ages 18 to 49 years (inclusive), who are HTNV and PUUV naïve (i.e., up to 12 subjects per group). The intended study sample for the study is 60 participants (i.e., 10 subjects per group). Due to attrition concerns, an additional 2 participants will be enrolled to each group to bring the total study sample to 72. Please refer to Section 5 for details on the relationship between the sample size and expected power of analyses.

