8. SAFETY EVALUATION

Safety analysis will include data collected from the Safety Population. Adverse event data will be listed individually (including intervention and outcome) (Listings 1.11.1, 1.11.2, and 1.11.3) and summarized by body system and preferred terms within a body system for each treatment group. Serious and/or unexpected AEs will also be discussed on a case-by-case basis. For the tabulation of the AEs by body system, a subject will be counted only once in a given body system. For example, a subject reporting nausea and diarrhea will be reported as one subject, but the symptoms will be listed as two separate AEs within the class. Therefore the total number of AEs reported within a body system may exceed the number of subjects within the body system reporting AEs. Tables 4.1 and 4.2 will present data about which groups ever experienced adverse effects.

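### The SAP's only between-group test of unsolicited AEs (Table 4.2) states neither the relatedness condition nor the 28-day window of the primary endpoint, and no SAP table shows that endpoint by group

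*SAP*

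**What the plan says.** SAP Section 3.3 lists among the primary endpoints "The occurrence of vaccine-related unsolicited AEs from the time of the first injection through 28 days following each injection". Protocol Sections 6.1 and 10.2 give the same definition.

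The between-group comparison is in SAP Appendix I: "TABLE 4.2: Safety Analysis Group Comparison: Ever Experienced Unsolicited Adverse Events". It has a percentage and 95% CI per group and pairwise two-sided Fisher p-values. Its title, rows and footnote mention neither relatedness nor a window. SAP Section 8 introduces it only by saying "Tables 4.1 and 4.2 will present data about which groups ever experienced adverse effects".

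On collection, Protocol Section 10.6.1 says "The time frame for the collection of AEs and SAEs begins at the first administration of investigational product through the end of the study". Under Protocol Section 8.1.4 the last clinic visit is Day 140, and the Day 220 contact is a telephone call for serious events only.

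On error control, Protocol Section 11.3 says "All statistical analyses will be made using a two-tailed" alpha of 0.05, and SAP Section 6.7 says "Multiplicity adjustments are not planned". SAP Section 5 calls all analyses exploratory and says the group sizes were not chosen to give adequate power.

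**The concern.** The plan defines one outcome as primary and attaches its p-values to another. Read literally, Table 4.2 counts a subject with a cold on Day 120 the same as a subject with a device reaction on Day 2.

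This matters because Protocol Section 10.3.2 records eschar, bleeding, tingling or numbness, and pigmentation change as unsolicited events. These could plausibly differ between the intradermal and intramuscular devices, so a real route difference may fall within this endpoint. If most subjects in every group have some unrelated unsolicited event, Table 4.2 has little room to show that difference, and its p-values may still be read as the unsolicited-safety comparison.

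**Working it through.** **1. Does any planned output show the defined endpoint by group?**

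| Output | Related only? | 28-day window? | By group? | Test? |
|---|---|---|---|---|
| Primary endpoint (SAP 3.3) | yes | yes | – | – |
| SAP Table 4.2 | not stated | none (ever) | yes | Fisher, pairwise |
| SAP Table 2.2 | has a related column | 32 days | no | none |
| SAP Tables 2.3.3 and 2.3.4 | split by relatedness | none | yes, but for unexpected AEs | none |
| Protocol 11.1.1, AEs by body system | no | none | yes | Fisher |

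No row meets all the conditions. This needs no assumed rate.

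**2. How much extra time does an unrestricted count cover?** The last dose is on Day 56, and 56 + 28 = Day 84. Routine collection runs to Day 140, so 140 − 84 = 56 further days are counted. The endpoint window is 84/140 = 60% of the period.

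**3. How common might unrelated events be?** The documents give no background rate for this trial. The nearest source is the earlier intramuscular study (Protocol Section 4.4.2.1.2): 31 subjects and 246 AEs, of which 96 were "considered related to injection, of which 87 (90.6%) were local reactions at the injection site".

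- Not related: 246 − 96 = 150.
- Remove every headache, muscle-ache and fatigue report, since these are solicited here: (5.7% + 3.3% + 3.3%) × 246 ≈ 30, leaving 120, or 120/31 ≈ 3.9 per subject.
- P(at least one), Poisson: 1 − exp(−3.87) ≈ 98% over that study. With strong clustering (negative binomial, k = 0.5): 1 − (1 + 3.87/0.5)^(−0.5) ≈ 66%.
- Scaled to Day 140, assuming that study followed subjects for about 236 days: 3.87 × 140/236 ≈ 2.30, giving about 90% (Poisson) or 58% (k = 0.5).

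The estimate is rough. The remaining 120 events may include laboratory AEs, which are a separate endpoint here, and other solicited types.

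**4. What does dilution do to the test?** Group size is from SAP Section 4.3 ("i.e., up to 12 subjects per group"), with two-sided alpha 0.05. Let r be the related rate and b the unrelated background, assumed independent and equal across groups. The counted proportion is p = 1 − (1 − b)(1 − r). At b = 50%, for example, 5% v 60% becomes 1 − 0.5 × 0.95 = 52.5% v 1 − 0.5 × 0.40 = 80%. Power is by full enumeration of the two binomials. All related rates are assumptions. The 29% is 9/31, the most subjects who could have had one of the 96 − 87 = 9 related non-local events in the earlier study.

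| Related rates | Group sizes | b = 0 (defined endpoint) | b = 50% | b = 70% |
|---|---|---|---|---|
| 5% v 60% | 12 v 12 | 78% | 17% | 6% |
| 10% v 60% | 12 v 12 | 64% | 14% | 5% |
| 5% v 29% | 12 v 12 | 15% | 4.5% | 2% |
| 10% v 60% | 12 v 22 (Group 6 at its protocol size) | 79% | 27% | 16% |

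**5. Is there a ceiling?** With 12 per group, 12/12 v 7/12 gives p = 0.037 and 12/12 v 8/12 gives p = 0.093. Once at least 8 of 12 subjects in each group have any unsolicited event, no such pair can reach 0.05, whatever the product does.

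The plan states no power or rate for this comparison, so there is no planned figure to reproduce.

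**The case against.** The strongest reply is that these are declared exploratory comparisons in an unpowered Phase 1 study, and that the right endpoint would often do little better. At 5% v 29%, the defined endpoint has only 15% power with 12 per group. That stands, and it limits what the added test can deliver. It does not explain why the p-values belong to an outcome other than the stated primary endpoint.

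Four stronger readings are tempting, and the documents do not support them.

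- *That Table 4.2 is the only between-group AE test.* This is true of the SAP only. Protocol Section 11.1.1 adds a Fisher comparison by body system. It is all-cause too, so it does not close the gap, although splitting by organ class separates some background illness from injection-site events.
- *That the sponsor chose to test all-cause events to the end of the study.* No text says so. It is inferred from a mock-up and one sentence that set no limits. The defect is an unspecified outcome.
- *That product differences will be hidden.* The loss depends on background and effect rates that the documents do not give. Related events also appear descriptively in Tables 2.2 and 2.3.3, and Protocol Section 11.1 promises summaries by relationship and study group, with unsolicited events handled similarly. A marked imbalance could show there.
- *That the all-cause test should be dropped.* Subjects and clinical staff are unblinded, so a test resting only on causality judgement would be open to bias. The all-cause comparison is a sound complement.

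**Conclusion.** The mismatch is a matter of document fact. Table 4.2 lacks both conditions of the primary unsolicited-AE endpoint, and no SAP table presents that endpoint by group. Dilution is likely but its size is not known. Under the assumed rates with 12 per group, power falls to between about a fifth and a third of its undiluted value at 50% background, and further at 70%. These figures rest on independence, equal background across groups and assumed related rates, with background gauged only loosely from one earlier study. They illustrate direction and rough scale and do not predict this trial's result. Because the comparisons are exploratory, a non-significant Table 4.2 would not establish similar safety, and neither would a non-significant test of the defined endpoint.

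**What to change.** Add to Table 4.2 a row giving n, %, 95% CI and Fisher p by group for this outcome: *at least one vaccine-related unsolicited AE with onset from first injection through 28 days after any injection*. Keep the all-cause comparison beside it, labelled as all-cause and with its time span stated.

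Two definitions need settling at the same time:

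- **Relatedness.** Table 2.3.3 counts possible, probable and definite as related. The DMID mapping in Protocol Section 10.4 and SAP Section 8.5.1 also counts unlikely. State one cut and use it in every table.
- **Window.** Reconcile the 32 days in Table 2.2 with the 28 days of the endpoint.

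The cost is SAP shell wording. Onset date and relationship are already collected (Protocol Section 10.3.1), so no new data are needed. The downside is one more exploratory, unadjusted set of p-values that rests on unblinded causality judgement, which is the reason to keep both rows.
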